# **PART 1: KEY INFORMATION**

Title\*: A Study of the 'Pawsitive' Impacts of Therapy Dog Visits with Adult Emergency

Department Pain Patients Level of Risk: \* Minimal risk

Expected Start Date: \* 2019-06-01
Expected End Date: \* 2019-11-30

If applicable, explain why this application is time sensitive: The RUH ED will move to its new location in November, 2019. We cannot collect data in two different locations with our control design. Also, our SCPOR funded researcher organizing the study and the data collection lead is only funded until November, 2019. We just received notice of our funding at the start of this month.

If this project will be conducted within schools, health regions, or other organizations, specify how you will obtain permission to access the site. Submit a copy of the certificate or letter of approval when obtained. Letter of approval has been obtained (see attached)				
If you do not plan t	to seek approval, provide a justification:			
Other Ethics A	pproval			
This project has ap Board(s) *	pplied for/received approval from another Research E	thics Yes No		
If 'yes', identify the	e other Research Ethics Board(s):			
Conflict of Inte	erest			
Confirm whether a	iny member of the research team or their immediate	family members will:		
1	benefits over and above the direct costs of conductine muneration or employment: *	ng the Yes No		
Receive significan	nt payments from the Sponsor such as compensation	in the form Yes No		

of equipment, supplies or retainers for ongoing consultation and honoraria: *	
Have a non-financial relationship with the Sponsor such as unpaid consultant,	
board membership, advisor or other non-financial interest: *	☐ Yes ☒ No
Have any direct involvement with the Sponsor such as stock ownership, stock	□ Vas ⊠ Na
options or board membership: *	∐ Yes ⊠ No
Hold patents, trademarks, copyrights, licensing agreements or intellectual	□ Vas ⊠ Na
property rights linked in any way to this project or the Sponsor: *	∐ Yes ⊠ No
Have any other relationship, financial or non-financial, that if not disclosed, could	□ Vas ⊠ Na
be construed as a conflict of interest: *	☐ Yes ☒ No
If yes was answered to any question(s), explain the personal benefit(s) and how the	conflict will be
managed:	

## **Part 2: PROJECT OVERVIEW**

# **Project Overview**

Summarize this project, its objectives and potential significance:

The goal of this unique 18 month study is to better understand the experiences of pain patients in the Royal University Hospital (RUH) Emergency Department (ED) to create excellence in health care. The purpose is to measure the impact of visiting therapy dogs on reducing ED patient pain. The background rationale is that pain is the primary reason individuals attend an ED, patient pain is generally not well managed in EDs, Saskatchewan EDs have among the longest wait times in the country, and anxiety associated with ED waiting can negatively impact patients' pain. Research suggests a therapy dog can change patients' perceptions of pain and its intensity and facilitate relaxation. The intervention will be examined for its impact on patients' sensory pain (i.e., physical pain severity), affective pain (i.e., emotional pain unpleasantness) and anxiety. It is important to find creative, low-cost ways to respond to patients attending the ED for pain. The primary objective of this study is to generate new health-related knowledge on the ED pain patient experience. The secondary objectives are to implement effective end-of-grant knowledge translation and dissemination strategies and undertake a successful model of collaborative, multidisciplinary research among researchers, patient advisors and system representatives, rooted in a One Health framework.

Provide a description of the research design and methods to be used:

St. John Ambulance Therapy Dog teams are comprised of a certified (tested and passed) therapy dog and handler. The goal of the St. Johns Ambulance therapy dog program is to offer support and comfort to individuals the dogs visit with. Five therapy dog teams commonly visit the RUH ED five days a week. The visits follow a standardized protocol (i.e., sign in, patients interact with the therapy dog, handlers share information about the dog). In this study therapy dogs will visit a convenience sample of consenting RUH ED pain patients five days a week. Each therapy dog team will participate once-a-week, for a 90 minute period, and during peak and low patient ED wait times (by day of the week and time). Participants will be over the age of 18, able to provide consent, attending the ED because of pain and want to visit with a therapy dog. These patients are located in the 'active area' of the ED in individual curtained-off spaces with beds; the patients are either waiting to be seen by a physician, have treatment in progress, or are admitted to hospital and waiting for a unit bed. A

control group will also be involved, with the same process and sample.

Data will be collected 3 days/ week (alternating with control days). Data will be collected in five steps, using quantitative psychometric measures that will not exceed 10 minutes. Patient pain will be measured with the Edmonton Symptom Assessment System (revised version) (ESAS-R) (numerical pain scale) and patient anxiety will be measured with biomarkers (heart rate, blood pressure) and the ESAS-R (anxiety, depression and overall wellbeing questions). The Human-Animal Interaction Scale (HAIS) will be applied to document the behaviour and amount of interaction between the therapy dog and patient. Quantitative data analysis using both descriptive and inferential statistical procedures will be conducted to examine distributions, relationships and differences among variables. Measures of outcome variables will be compared between pre- and post-therapy dog intervention and the influence of moderator variables, such as gender, will be examined. The HAIS score will indicate the quantity of positive human-animal interaction.

Control group data will be collected 2 days/ week (alternating with animal testing days) with a goal of 8 samples per day. The data collection will occur in two stages. First, patient pain will be measured with the Edmonton Symptom Assessment System (revised version) (ESAS-R) (numerical pain scale) and patient anxiety will be measured with biomarkers (heart rate, blood pressure) and the ESAS-R (anxiety, depression and overall wellbeing questions). The HAIS scale will not be administered during the control as there will be no animal interaction. Control days require two research assistants who will obtain consent using a deceptive consent form which will explain that this is a pain study but will omit any information regarding therapy dogs. Once all measures are taken the participants will be explained the deception and asked to sign the true consent form.

All of our team members will meet on a monthly basis. The team represents a solid compliment of expertise, experience and knowledge (contributing from data collection through to end-of-grant knowledge translation). This will enable the team to fully deliver on the project goal, purpose and objectives. The outcomes of this study will be meaningfully translated and disseminated to improve the health care of RUH ED pain patients with peer reviewed publishing, RUH monitor adverts and webinar, and a news release. The clinical relevance of this study is that the outcomes will offer a complementary understanding of quality health care for ED pain patients. To date there have been no studies of therapy dogs in EDs in Canada.

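### Dog visits on five days a week are not reconciled with two control days a week, and the alternation rule can tie weekday to study arm

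*Protocol*

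**What the plan says.** All references are to the Protocol.

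- **Dog visits (Project Overview).** The usual service is described as "Five therapy dog teams commonly visit the RUH ED five days a week". For the study itself: "In this study therapy dogs will visit a convenience sample of consenting RUH ED pain patients five days a week". On each team's share: "Each therapy dog team will participate once-a-week, for a 90 minute period", to be spread "during peak and low patient ED wait times (by day of the week and time").
- **Dog-arm data (Project Overview).** "Data will be collected 3 days/ week (alternating with control days").
- **Control data (Project Overview).** "Control group data will be collected 2 days/ week (alternating with animal testing days) with a goal of 8 samples per day". The section adds that the interaction scale is not used for controls because they interact with no animal. It intends the arms to be alike: a "control group will also be involved, with the same process and sample".
- **Control condition elsewhere.** Participant Recruitment says that controls will not have a dog visit. Consent Process justifies the deception on control days by the need for pain and anxiety to be free of any influence from knowing about the dogs.
- **Dogs outside the study.** Risks and Benefits says that the dogs have visited this ED for three years independently of the study. Participant Recruitment says that any ED patient may have a visit, whether or not they take part.
- **Limits on contact.** Patients are in "individual curtained-off spaces with beds", each team takes part for 90 minutes, and Risks and Benefits says that patients are approached only with their consent.

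**The concern.** There are two linked problems.

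**Dogs in the ED on control days.** The control condition is stated, but not how it is kept. Dog contact between a control's two measurements would pull the arms together. Merely seeing a dog would defeat the stated reason for the deception. If contact is not recorded, no later analysis can examine it.

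**Weekday and arm.** Whole days, not patients, are assigned to dog or control, and the document gives no rotation or randomisation of days. The Project Overview itself links wait times to day of the week and time, and its rationale links anxiety about waiting to pain. A weekday effect that acts equally on the before and after measurements cancels in a change score. One that acts on the short-term change, for example through patients being seen or moved sooner on quieter days, does not cancel. On a fixed calendar it could not be told apart from a dog effect.

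Both are matters of conduct. An analysis plan cannot repair them once the data are in.

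**Working it through.** **1. Visiting days against data days.** From the Project Overview: five teams, each once a week, over five days, so 5 × 1 = 5 sessions, or one a day. Dog data are taken on 3 days, so 5 − 3 = 2 visiting days a week fall outside dog-data collection. Control days number 2.

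- If the five data days (3 + 2) are the five visiting days, both control days are visiting days.
- If other days of the week may be used, control days are free of dog visits only when they are exactly the two days without a visit. The Protocol does not say that they are.

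**2. What literal alternation implies.** There are C(5,2) = 10 ways to place two control days in a five-day week. Only one alternates throughout: dog, control, dog, control, dog. Carrying the alternation over into the next week would give control, dog, control, dog, control, which is 2 dog and 3 control days and breaks the stated 3 and 2. Keeping 3/2 on the same five weekdays therefore repeats one pattern. If those weekdays were Monday to Friday, control would always be Tuesday and Thursday.

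**3. Can arm be separated from weekday?** Take a model with five weekday columns and one arm column.

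| Calendar | Rank (of 6) | Arm separable from weekday? |
|---|---|---|
| Fixed dog-control-dog-control-dog | 5 | No |
| Five-week rotation (see fix) | 6 | Yes |

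**4. Illustrative size of a weekday effect.** The Protocol gives at least 122 in both groups, without SD, effect size, power or significance level, so that figure cannot be reproduced. Assumptions: 122 per arm, a two-arm comparison of change, two-sided 5%, 80% power.

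- Standard error in SD units: √(2/122) = 0.128. Detectable difference: 2.80 × 0.128 = 0.36 SD.
- Let b be the difference in change between the two sets of weekdays (in SD) and s the difference between arms in weekday mix (1 = full aliasing, 0 = balanced). Then k = b·s / 0.128, and with no dog effect the rejection rate is Φ(−1.96 + k) + Φ(−1.96 − k).

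| b | s = 1 | s = 0.5 | s = 0 |
|---|---|---|---|
| 0.1 SD | k = 0.78, 12% | k = 0.39, 7% | 5% |
| 0.2 SD | k = 1.56, 35% | k = 0.78, 12% | 5% |

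The sample-size wording could also mean 122 in total. With 61 per arm the standard error is √(2/61) = 0.181, and the s = 1 rates become 9% and 20%.

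**5. Illustrative size of contact.** Let d be the share of the dog-control difference lost (share of controls in contact × share of the effect that they receive). With 122 per arm, power is Φ(2.80(1 − d) − 1.96): 76% for d = 0.05 and 71% for d = 0.10, against 80% with no contact.

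**The case against.** The strongest reply is that the text has an ordinary reading. It first describes visits on five days and then data collection, with dog-arm data on three of them. That is coherent, and the Protocol promises controls no interaction rather than an ED without dogs. It also does give a rule for days, namely alternation. Curtained spaces, 90-minute sessions and approach on consent make contact unlikely. The sentence that all ED patients may have a visit can be read as protecting those who decline the research, not as permission to visit controls between measurements. Weekday aliasing needs fixed weekdays and literal alternation, and the Protocol names no weekday. The error rates rest on assumed shifts.

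Much of this stands. A reader might infer that the Protocol lets dogs visit controls, that control days are necessarily visiting days, or that weekday and arm are certainly confounded. The documents support none of these. The no-contact condition is written down twice, a seven-day week leaves room for control days without visits, and a rotating calendar would remove some or all of the aliasing.

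Two things remain. The ordinary reading still leaves dogs in the ED on control days unless those are the two non-visit days, and no operating procedure addresses this although the Consent Process depends on controls being unaffected by knowledge of dogs. And the one rule for days, applied literally to the same five weekdays, produces full aliasing. Using two fixed non-visit days as control days would avoid contact but tie weekday to arm in the same way.

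**Conclusion.** The point holds as an unreconciled passage plus a weak allocation rule, and it should be fixed before data collection. Five-day study visits are not squared with two control days a week, and the no-contact condition has no procedure behind it. The alternation rule leaves open, and on a fixed five-day calendar forces, a complete tie between weekday and arm.

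Contact with or sight of a dog on control days is possible, not demonstrated. The aliasing depends on the same weekdays being used each week. The size is an illustration only: 12% or 35% false positives for a weekday difference in change of 0.1 or 0.2 SD, under full aliasing, 122 per arm and a two-sided 5% test. The documents do not show that a weekday difference of any size exists.

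**What to change.** (a) Reconcile Project Overview, Risks and Benefits, Participant Recruitment and Consent Process on whether dogs attend on control days and, if they do, how control collection is kept apart from visits.

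(b) Replace simple alternation with a rotating or randomised calendar that keeps three dog and two control days every week, with the same time windows in both arms. If Monday to Friday is used, a five-week cycle of control days Tue/Thu, Mon/Wed, Wed/Fri, Mon/Thu, Tue/Fri gives every weekday 2 control and 3 dog days.

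(c) At debriefing, record whether the control participant saw or visited a dog that day, for a sensitivity analysis. On a Monday-to-Friday visiting schedule the rotation does not remove dogs from control days, so this record is needed. Moving volunteer visits out of the control window is optional, where the programme can do so; it runs independently of the study.

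Cost: some scheduling work and one extra question. Strict day-by-day alternation is given up in four of the five weeks of the example cycle. No extra patients or days are needed. Two cycles (ten weeks) give 20 control and 30 dog days, so 122 per arm needs 122/20 = 6.1 controls per control day, against the goal of 8, and 122/30 = 4.1 patients per dog day. Ten weeks fit within the 153 days (21.9 weeks) from 1 June to 31 October 2019, before the ED's November move.

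### The only outcome contrast the protocol names is before versus after the dog visit; the dog-versus-control comparison is implied but not stated, and the controls' second measurement has no stated time.

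*Protocol*

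**What the plan says.** All places are in the protocol.

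- **Aim** (Project Overview): "The purpose is to measure the impact of visiting therapy dogs on reducing ED patient pain".
- **Named contrast** (Project Overview, design and methods): "Measures of outcome variables will be compared between pre- and post-therapy dog intervention", followed by moderators such as gender. The only other analysis wording is general: inferential procedures will look at "relationships and differences among variables".
- **Signs that a group comparison is meant:** Part 1 explains the time pressure with "We cannot collect data in two different locations with our control design". Project Overview says that a "control group will also be involved, with the same process and sample". Participant Recruitment asks for at least 122 in both groups. Consent Process justifies deceiving controls so that their pain and anxiety are not influenced by knowing about the dogs.
- **Control data collection** (Project Overview): "The data collection will occur in two stages". The first stage is ESAS-R pain, anxiety, depression and wellbeing, with heart rate and blood pressure. No second stage is described. The text goes on to the HAIS, consent and debriefing: "Once all measures are taken the participants will be explained the deception and asked to sign the true consent form".
- **Timing** (Duration and Location of Data Collection Events): heart rate and blood pressure are taken before, during and 15 minutes after the visit. The pain and anxiety questions are asked before it and again 15 minutes after it. Participant Recruitment confirms that controls do not meet a dog.

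**The concern.** A change from before to after the visit mixes any effect of the dog with whatever else happens in that interval. Some patients "have treatment in progress", which could ease pain. The protocol's own rationale is that anxiety from waiting can make pain worse. The medication check in Participant Recruitment covers the hour before the visit, not the time during or after it. So the pre-post contrast could show a benefit that is not there or hide one that is.

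The control group is the remedy, but it removes shared change only if controls are measured again after a similar elapsed time. When research assistants take that second measurement is a data-collection procedure. A later analysis plan cannot supply it if the staff had no set time to work to.

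**Working it through.** **1. The plan's own figure.** The only number to start from is 122 per group (Participant Recruitment). The protocol attributes it to pilot data and gives no significance level, power, effect size or SD, so it cannot be rebuilt from stated inputs. Nor does it show which contrast was meant. Assuming two-sided 5% and 80% power (1.960 + 0.842 = 2.802):

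- two groups of 122: 2.802 × √(2/122) = 0.36 SD;
- paired, 122 patients: 2.802 / √122 = 0.25 SD of change.

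Either is plausible. Nothing here shows 122 to be wrong.

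**2. What the named contrast does when the dog has no effect.** Inputs: n = 122 dog patients; two-sided 5%, assumed; a background drift δ in units of the SD of change, assumed because the protocol gives none. The paired t statistic is noncentral t with 121 degrees of freedom and noncentrality δ√122 (√122 = 11.05). The critical value is 1.980.

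| Assumed drift δ | δ√122 | Chance of a significant result |
|---|---|---|
| 0.05 | 0.55 | 8.5% |
| 0.1 | 1.10 | 19% |
| 0.18 | 1.98 | about 50% |
| 0.2 | 2.21 | 59% |
| 0.3 | 3.31 | 91% |

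From δ = 0.1 upwards nearly all of these results lie in the direction of the drift. Falling pain would look like a benefit. Rising pain would look like harm or would offset a real benefit.

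**3. What a comparison with controls does.** With the same drift in both groups over a matched interval and independent patients, simulation at 122 per group and zero dog effect gave rejection rates of 4.9% to 5.2% for change scores and 4.9% to 5.3% for a baseline-adjusted comparison (pre-post correlation 0.6 assumed), at drifts of 0.1 to 0.3 SD. Two conditions sit behind that result.

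- *Matched timing.* If unequal intervals leave a difference in drift between groups of 0.1, 0.2 or 0.3 SD (assumed), the noncentrality is that difference × √(122/2), that is 0.78, 1.56 or 2.34. The two-sample test then rejects 12%, 34% or 65% of the time.
- *Independence within days.* Groups are allocated by day. Take 8 patients a day (the control goal in Project Overview, assumed for dog days too) and an assumed within-day correlation of 0.02 or 0.05. The variance inflation is 1 + 7 × 0.02 = 1.14 or 1 + 7 × 0.05 = 1.35. A test that ignores day then rejects about 6.6% or 9.2% of the time.

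**4. Can the control interval be derived from the text?** In the dog group, baseline to second questionnaire is roughly the visit length plus 15 minutes. No visit length per patient is given; the 90 minutes in Project Overview is a dog team's whole session. Controls have no visit from which to count. The heart rate and blood pressure reading taken during the visit has no stated control counterpart either. The interval cannot be derived.

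**The case against.** **The group analysis can be left to a SAP.** The exact model can. The quoted sentence does not call itself the primary or only analysis, and pre and post values are the raw material of a group comparison of change. A reader might infer that the team means to analyse the dog group alone and ignore its controls. The documents do not support that: the control design, the sample required in both groups and the deception rationale all point to a comparison. What stands is that the protocol does name a contrast, and the one it names does not answer its stated aim.

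**Controls are plainly measured twice.** A reader might infer from the missing second stage that there is no second control measurement. That reading is strained. Debriefing and re-consent are not data collection, they come after all measures, and the control process is said to be the same. Re-measurement is the natural reading. What stands is that it has no time.

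**Unmatched intervals can be adjusted for.** Partly, and under assumptions, if elapsed times are recorded and overlap between groups. No recording of clock times is mentioned in the visible text.

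**Timing may be in attached forms that are not shown.** Possibly. The statement here is limited to the visible text.

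**The drift figures are assumed and price an analysis that is probably not the intended one.** Correct. They illustrate why the named contrast should not carry the conclusion; they do not predict this trial's error rate.

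**Conclusion.** The point holds as a should-fix. The one stated contrast cannot measure the dogs' impact, the comparison that can is only implied, and the controls' re-measurement has neither a time zero nor an interval in the visible text.

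The size depends on the assumed drift and on reading the pre-post test as the dog effect. Even 0.18 SD of change would make it significant about half the time with no dog effect. A comparison over matched intervals removes drift shared by both groups. It does not remove differences between dog days and control days, and its 5% level holds only if patients within a day are independent or day is accounted for.

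**What to change.** 1. In Project Overview, where the analysis is described, state that the effect of the dog visit is the dog-versus-control difference in ESAS-R pain (and likewise anxiety) at the second measurement, adjusted for the baseline already collected. Report within-group pre-post changes descriptively. The exact model can go in the SAP.
2. In the control paragraph, describe stage two: controls are re-measured at an elapsed time from baseline that matches the dog group's, that is the usual visit length, which the team should state, plus 15 minutes.
3. Record the clock times of the measurements in both groups.
4. Say whether controls have a counterpart to the heart rate and blood pressure reading taken during the visit.
5. State as a limit that allocation by day leaves differences between dog days and control days in the comparison.

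The cost is some wording, a set re-measurement time for the research assistants to keep, and clock times on the data sheets. No extra patients are needed.

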#### **PART 4: RECRUITMENT AND CONSENT**

# **Participant Recruitment**

Indicate the expected number of participants and provide a brief rationale for the number:

A sample size of at least 122 in both the control and animal intervention is required to detect statistically significant results based on information collected on patient response in the pilot study.

Describe the criteria for including participants:

Participants will be over the age of 18, able to provide consent, attending the ED because of pain and want to visit with a therapy dog. These patients are located in the 'active area' of the ED in individual curtained-off spaces with beds; the patients are either waiting to be seen by a physician, have treatment in progress, or are admitted to hospital and waiting for a unit bed. Participants will also be willing to visit with a therapy dog team (although the control group will not be visiting with a dog).

Describe the criteria for excluding participants:

The RA will access the patient's Medication Administration Record (MAR) to confirm non-administration of pain medications (specifically immediate release acetaminophen and opioid analgesics) within the hour prior to the visit. This step is included to prevent confounding the potential effect of the therapy dog intervention on pain outcomes.

Provide a detailed description of the method of recruitment, such as how and whom will identify and contact prospective participants:

RA #1 will identify patients who are verbally coherent and interested in visiting with a therapy dog. Consent will be obtained from pain patients to participate in the study. All ED patients can visit with a therapy dog, regardless of study participation. The RA will access the patient's Medication Administration Record (MAR) to confirm non-administration of pain medications (specifically immediate release acetaminophen and opioid analgesics) within the hour prior to the visit. This step is included to prevent confounding the potential effect of the therapy dog intervention on pain

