**Data collection tools** 

- -ESAS-R (indicate on picture; scale 1-10)
- -Main reason for attending the ED
- -Heart rate and blood pressure
- -ESAS-R numerical scale (anxiety, depression, wellbeing)
- -Patient demographics
- -HAIS form

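### Moderators such as gender are tied to the dog group's before-after change, which cannot separate who benefits from the dog from who would have changed anyway

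*Protocol*

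**What the plan says.** All of this is in the Protocol; no SAP is to hand.

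- **The stated contrast** (Project Overview): "Measures of outcome variables will be compared between pre- and post-therapy dog intervention". The same sentence continues that "the influence of moderator variables, such as gender, will be examined". Gender is the only moderator named, as an example.
- **The general statement** (Project Overview): descriptive and inferential procedures will be used "to examine distributions, relationships and differences among variables". It names no groups and no model.
- **The control group** (Project Overview): a "control group will also be involved, with the same process and sample". Control collection has two stages, of which only the first is spelled out.
- **How groups are formed** (Project Overview): by day, from a convenience sample. Dog data are collected on three days a week; for controls, "Control group data will be collected 2 days/ week (alternating with animal testing days) with a goal of 8 samples per day". No randomisation of patients or days is described.
- **Size** (Participant Recruitment): "A sample size of at least 122 in both the control and animal intervention is required", with reference to the pilot study. Alpha, power, effect size and SD are not given.
- **Data** (Data collection tools): the list includes "Main reason for attending the ED" and patient demographics, without saying which demographics.

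**The concern.** A moderator of treatment effect is a variable across which the difference between treated and untreated patients changes. A variable that predicts change among treated patients alone does not show this. The eligible patients are waiting, under treatment or already admitted, and their pain can move between the first measurement and the one 15 minutes after the visit for reasons unrelated to a dog. If men and women differ in starting score, in natural course or in response to care, the dog group will show a gender difference in change even if the dog does nothing.

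At stake is whether a reported finding about who benefits from dog visits is about the dog at all. The trial recruits the control group that would answer the question, but the stated contrast does not use it.

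**Working it through.** **1. The plan's own figure.** I read 122 as per group. It cannot be reproduced uniquely, because its inputs are not given. With two-sided 5% and 80% power (assumed), n = 2(1.960 + 0.842)² / d². At d = 0.36 SD this is 2 × 7.849 / 0.1296 = 121.1, so 122. Other sets come close: 90% power gives 123 at d = 0.415. The number is neither confirmed nor refuted, and the point does not depend on it.

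**2. Gender test inside the dog group, no dog effect.** Assumptions, none from the Protocol: SD of pain change 2 to 2.5 points; 61 men and 61 women in each group; natural course differing by gender by g points.

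SE = SD × √(1/61 + 1/61) = SD × √(4/122) = SD × 0.181, that is 0.362 (SD 2) or 0.453 (SD 2.5).

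Probability of significance = Φ(g/SE − 1.96) + Φ(−g/SE − 1.96).

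| g (points) | SD 2 | SD 2.5 |
|---|---|---|
| 0 | 0.05 | 0.05 |
| 0.5 | 0.28 | 0.20 |
| 1.0 | 0.79 | 0.60 |
| 1.5 | 0.985 | 0.91 |

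**3. Group-by-gender interaction.** The same g appears in both groups, so its expected value is g − g = 0 and the test rejects about 5% of the time. A simulation of 5,000 trials at g = 1.0 and SD 2 gave 0.776 for the dog-only test and 0.051 for the interaction. The cancellation assumes that the gender gap in natural course is the same on dog days and control days.

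**4. The before-after contrast has the same weakness.** With an average natural fall of 0.5 points and no dog effect, SE = SD/√122 = 0.181 to 0.226. The test is significant with probability 0.79 (SD 2) or 0.60 (SD 2.5).

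**5. Precision of the interaction.** SE = SD × √(4/61) = 0.256 SD. Detectable at 80% power: 2.80 × 0.256 = 0.72 SD, or about 1.4 to 1.8 points at SD 2 to 2.5. Power at 0.36 SD: 1 − Φ(1.96 − 0.36/0.256) = 0.29.

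**6. Why adjustment belongs in a comparison by day.** Suppose a patient factor shifts change by 1 to 2 points and its frequency differs between day groups by 10 to 20 percentage points (both assumed). Bias = shift × imbalance = 0.1 to 0.4 points. With SE = SD × √(2/122) = 0.256 to 0.320 points, the unadjusted two-sided type I error is 0.06 to 0.35 instead of 0.05.

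**The case against.** **The dog-only reading is an inference.** The moderator clause names no arm and no model. The general statement is wide enough to cover a controlled comparison, and the control group and the two-group sample size show that one is intended. That stands as far as it goes: the Protocol does not exclude it. But the general statement fixes nothing, and the one sentence that fixes a contrast has no meaning for patients without a dog visit. An SAP that followed it would carry the fault forward.

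**Stronger readings that the document does not support:**

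- A reader might infer that patient variables serve only as moderators and that case mix goes uncorrected. The text says neither. A covariate list is commonly left to an SAP. The Protocol also limits confounding by checking for recent analgesics, applying common entry criteria, alternating days and spreading dog visits over peak and low waiting times.
- A reader might count low power for moderators as an error. The Protocol claims no such power, and lacking it is usual.
- A reader might expect baseline adjustment to remove any bias from unequal starting scores. That holds for chance imbalance. Here groups are formed by day, and dog-day patients are told of the dog before the first measurement while controls are not. The baseline itself may be affected, and change-score and baseline-adjusted answers can differ.
- A reader might assume that age and gender are listed as collected in both groups. The list says only demographics, and the account of control measurements mentions neither these nor the reason for attending, although the shared process may cover them.
- A reader might fear that a false gender effect would decide who is offered visits. Participant Recruitment says that any emergency department patient may have one.

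**Conclusion.** The point holds for the contrast that the Protocol states. Comparison before and after the dog, with moderators attached to it, cannot separate effect modification from natural course, regression to the mean or response to care. In the illustration the false-positive rate of the dog-group gender test is about 20% to 99%, against about 5% for an interaction that includes controls. Those figures rest on an assumed change SD of 2 to 2.5 points, a gender difference in natural course of 0.5 to 1.5 points, 122 per group and an even gender split. With no gender difference in natural course the dog-only test also keeps its 5%, so a misread gender effect is a risk and not a certainty.

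The adjustment point is narrower: the Protocol does not state adjustment, and because groups are formed by day without described randomisation, it should be specified. The Protocol does not reject it.

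**What to change.** Reword the analysis sentence in Project Overview to say that:

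1. outcomes are compared as change in the dog group versus change in the control group;
2. moderators are tested only as group-by-moderator interactions that include the controls, reported with confidence intervals and labelled exploratory, with no conclusion drawn from subgroup p-values within the dog group;
3. the dog-versus-control model adjusts for main reason for attending and the collected demographics (age and gender if recorded in both groups);
4. results are shown with and without adjustment for the baseline score, because dog-day patients know of the dog before it is measured.

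The cost is wording, provided that controls have the second measurement, the reason for attending and the demographics recorded; the Protocol should confirm this. The downside is that moderator results become openly exploratory and imprecise: the detectable interaction is about 0.72 SD with 122 per group, assuming two-sided 5%, 80% power and an even split. Adjustment cannot remove selection on factors that were not measured.
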